#### JHM IRB - eForm A – Protocol

- Use the section headings to write the JHM IRB eForm A, inserting the appropriate material in each. If a section is not applicable, leave heading in and insert N/A.
- When submitting JHM IRB eForm A (new or revised), enter the date submitted to the field at the top of JHM IRB eForm A.

#### \*\*\*\*\*\*\*

#### 1. Abstract

a. Provide no more than a one-page research abstract briefly stating the problem, the research hypothesis, and the importance of the research.

Based on preclinical research and emerging human research, cannabidiol (CBD; a major constituent of the cannabis plant) is a promising pharmacotherapy for the treatment of opioid withdrawal. Most recently, CBD decreased cue-induced craving and anxiety (two common withdrawal symptoms) among abstinent heroin-dependent individuals relative to placebo. Despite promising data, there are no funded studies which are prospectively designed to rigorously test the ability of CBD to decrease opioid withdrawal symptoms. As of June 2018, Epidiolex, an oral formulation of plant-derived pure CBD, has been approved by the U.S. Food and Drug Administration (FDA) for treating severe forms of epilepsy and can be prescribed for other off-label indications. Epidiolex has a low side effect and high safety profile. Preclinical evidence has suggested that the cannabinoid system contributes meaningfully to the opioid withdrawal symptome and withdrawal symptom severity. Given the recent FDA approval of Epidiolex, and a growing interest to develop existing pharmaceuticals to address issues related to OUD and its recovery, we are proposing a pilot study to examine the safety of Epidiolex in a human laboratory model of clinically relevant withdrawal. Results may be used to support an R01 grant application to more closely examine this hypothesis.

#### 2. Objectives

The objective of this research study is to collect data to support a NIDA grant application. Data collected for this study will establish: (1) the safety of administering two dosing regimens of Epidiolex within our withdrawal paradigm and (2) the feasibility of our withdrawal paradigm for demonstrating clinically meaningful increases in withdrawal.

**3. Background** (briefly describe pre-clinical and clinical data, current experience with procedures, drug or device, and any other relevant information to justify the research)

The increasing prevalence of opioid use disorder (OUD) is a public health crisis contributing to substantial economic and societal burden. The treatment of OUD, even with the most efficacious interventions, is characterized with high rates of relapse (i.e., > 50% relapsed within 6 months of treatment initiation). Managing withdrawal is critical for ensuring successful treatment retention and outcomes . Adjunctive pharmacotherapy is one way to address persistent opioid withdrawal symptoms and craving. Based on preclinical research and emerging human research, cannabidiol (CBD; a major constituent of the cannabis

plant) is a promising pharmacotherapy for the treatment of OUD. There is preclinical support that the endocannabinoid system is influential in the expression of opioid withdrawal. Cannabinoid type 1 (CB1) receptors are co-localized with mu-opioid receptors and cannabinoid agonists and endocannabinoid catabolic enzyme inhibitors have all shown evidence for opioid withdrawal suppression.

Over the last 40 years, preclinical evidence has accumulated indicating that CBD can mitigate symptoms of opioid withdrawal and decrease opioid seeking behavior in rodent models. In clinical research, retrospective analyses indicate that the use of cannabis products may be helpful for increasing opioid treatment retention. Two human lab studies (N=6 and n=42) on this topic demonstrated that a single dose of oral CBD decreased cue-induced craving and anxiety (two common withdrawal symptoms) among recently abstinent heroin-dependent individuals relative to placebo. In an effort to further characterize the clinical utility of CBD, we recently conducted a crowdsourcing survey study which determined that individuals with OUD with CBD use indicated that CBD helped mitigate the following opioid withdrawal symptoms: anxiety (76%), sleep problems (45%), restlessness (36%), and/or bone/muscle aches (36%).

Despite promising data, there are no funded studies which are prospectively designed to rigorously test the ability of CBD to decrease opioid withdrawal symptoms. As of June 2018, Epidiolex, an oral formulation of plant-derived pure CBD, has been approved by the U.S. Food and Drug Administration (FDA) for treating severe forms of epilepsy and can be prescribed for other off-label indications. In September of 2018, the DEA determined Epidiolex was a schedule V drug, further reducing barriers to conduct research with this promising pharmacotherapy. Epidiolex is remarkable for its wide safety profile alone and with opioids and its negligible abuse liability and is therefore appealing to use among high-risk clinical populations. Therefore, we plan to conduct a pilot study to establish the feasibility of our withdrawal paradigm and the safety of cannabidiol to treat withdrawal in a controlled setting. Within this context, we have incorporated two cue-attentional bias tasks which will allow us to identify the mechanisms by which CBD may reduce cue-induced craving and anxiety and whether changes in cue-reactivity influences suboptimal decision making. First, the visual probe task will expose participants to opioid-related and neutral cues and evaluate the role of these cues in attentional bias. This protocol will include two periods of exposure to opioid-related cues. Length of visual cue-exposure represent distinct assays for attentional bias; cues shorter than 200 ms measure automatic processing, cues longer than 500 ms measure controlled attention processing. Previous research has shown CBD influences automatic processing for cigaretterelated cues but not controlled processing. To date, this effect has not been studied for opioid-related cues. The second cue-task will evaluate whether the presence of opioid-related cues influence decisions about money. This will allow us to evaluate whether CBD impacts not only influences cue-reactivity but also related suboptimal decision making. While participants complete this task, we will also collect eye tracking data using the Gazepoint eye tracking device, which tracks eye movement on a computer screen with a machine-vision camera. These data may support a larger NIH grant application to study the efficacy and mechanisms of cannabidiol to treat opioid withdrawal in a rigorously controlled lab study.

#### 4. Study Procedures

a. Study design, including the sequence and timing of study procedures (distinguish research procedures from those that are part of routine care).

Study Design Overview: This study is a within-subject comparison of placebo and 800 mg of CBD. Participant will attend two residential sessions. Participants will receive active drug during one session and placebo on the other. The sequence of the sessions (Placebo, Active or Active, Placebo) will be randomized for all participants. Each of the two inpatient sessions will last 3-days /2-nights and will be scheduled at least one week apart. During the sessions, participant's will not take their regular daily methadone dose in order to produce an abstinence-induced withdrawal syndrome, which will allow

researchers to replicate realistic elevations in withdrawal symptoms under controlled laboratory conditions. This inpatient study design will provide a mechanism for rigorously assessing the initial feasibility and safety of CBD to mitigate clinically-relevant opioid withdrawal symptoms among individuals with opioid use disorder. Participants will take the study drug (800mg CBD/20mL) once every 12 hours for a total of 4 doses. This dosing regimen has been selected based upon evidence that four doses are required for Epidiolex to reach steady-state levels and that this dosing regimen is well-tolerated (23). Following study drug administration, participants will complete standardized opioid withdrawal measures and a behavioral task that can assess whether CBD reduces opioid valuation. At the end of the study, participants will be provided with their routine dose of methadone and transitioned back into methadone treatment. This model is a scientifically rigorous and feasible way to conduct this initial assessment and will provide the efficacy and safety data necessary to support a more thorough examination of CBD for opioid withdrawal management. This provides an expedient and cost-efficient way to collect the data necessary to support a formal NIDA R01 grant submission.

Recruitment/Screening. Participants will be recruited through methadone clinics using our established and successful methods, and through respondent driven sampling. We will provide incentives (\$10) to participants who refer a potential participant to the study who completes a screening visit. Individuals will complete a phone-screen for initial eligibility requirements and be invited for a remote consenting and screening visit. During the COVID-19 crisis, participants will be consented virtually. Participants will be able to review the consent form electronically using a secure IRB compliant method, and will be able to securely sign and submit the form after they have been provided ample time to read and ask questions related to the protocol. Participants will promptly receive an electronic form of the consent and can also receive a printed version via mail, at their request. Virtual consenting will follow IRB guidelines for virtual consenting procedures and will occur prior to any data collection.

When possible, we will use DocuSign, the Institution's approved and 21 CFR Part 11-compliant software, to obtain a secure electronic signature. Once the IRB approves this process, we will use the IRBapproved consent form(s) as the base for the DocuSign template. The IRB-approved document will not be altered other than to overlay locations where signatures, initials, dates or other DocuSign fields will be added to create the study-specific DocuSign template. We will send the consent to the participant via DocuSign, providing a participant-specific code in advance of sending the document via DocuSign, that will be required when the participant accesses and signs the consent. The consent discussion may take place via phone or video conference (e.g. Zoom). Participants will be given adequate time to consider the research study and ask questions prior to signing the consent form. When ready to sign, the participant will enter their code, verifying that the person signing the consent is the person that we spoke with previously, and sign the consent within the DocuSign system. Once the participant has electronically signed, the study team member obtaining informed consent will be notified that the electronic form is ready for his or her signature. Once signing is completed by all parties, both the study team and the participant can download the signed consent as a PDF. The study team will also have access to the audit log and the Certificate of Completion.

Self-report portions of the screen, including several questionnaires related to their medical and mental health and drug use history, will be done virtually (via phone or Zoom) with study staff. For persons who do not have access to phones or when participant privacy might be challenging (e.g., for persons without stable housing), we will conduct self-report portions of the screen in a private room at the BPRU with Zoom connection to study staff in another room, to minimize participant/staff interaction. If deemed eligible based on self-report and interviewer-based questionnaires, participants will be scheduled to complete a brief in-person medical assessment consisting of a blood draw that will be tested for medical eligibility and a medical history and physical. Participants will also provide a urine sample to be tested for

evidence of illicit opioid and other drug use and pregnancy (if applicable). Participants will also complete computerized tasks (e.g., Visual Probe Task and the Cue-concurrent Choice Task) to characterize baseline drug cue reactivity. Participants will sign a medical release which will allow research staff to contact the participant's provider to confirm (1) methadone maintenance dose and length of dose. All participants will be asked to sign a contraception contract in which they will agree to use an effective form of birth control for up to 30 days following the final session day.

#### Session Procedures.

Description of procedures to minimize risk during the COVID-19 pandemic for in-person sessions: It is not possible to conduct a portion of the screening and the inpatient protocol remotely due to the need to collect biological measures (e.g., blood, urine) for eligibility determination and to have continuous medical supervision and care during the supervised taper. However, there are specific safety procedures that will be put into place to minimize person-to-person contact in the context of the COVID-19 pandemic. First, during all in-person sessions, all participants will be required to wear a properly fitting face surgical grade mask while in the laboratory. The exception to this policy will be when the participant is alone in their residential room at the Clinical Research Unit (CRU) with nobody else present. Facemasks which meet these requirements will be provided to participants at no cost. Second, participants will be asked about potential COVID-19 symptoms upon arrival to each session and possible exposure to COVID-19. Any subject who arrives reporting symptoms indicative of COVID-19 per the JHU clinical screening algorithm will be required to return home and participation will be paused for at least 2 weeks after which a health care professional must clear a return to participation (e.g., with a negative COVID-19 test). Third, participants must adhere to the CRU policies for COVID-19 which are uploaded in the supplemental document section. This will be provided to participants at a screening visit and/or the first day of their enrollment into the residential portion of the study.

The CRU policies stipulate that participants must remain in their residential rooms unless completing study related activities that must take place in another room (i.e., electrocardiograms). In order to address issues related to isolation or boredom, participants will have access to various recreational activities in their room including video games and stationary bicycling. Participants will also be allowed to bring materials from their home including books and magazines.

This will be a within subject comparison. Each participant will attend two 3-day inpatient sessions during which they will receive active drug during one session and placebo on the other. The placebo will be a flavor-matched cherry liquid syrup. 2 syringes of 10mL of Study Drug + Flavored syrup (4mL Epidiolex, 6mL flavored syrup per syringe) and 2 syringes of 10mL Placebo (flavored syrup) will be administered via the oral route under double-blind conditions. The sequence of the sessions (Placebo, Active or Active, Placebo) will be randomized and counter-balanced for all participants. Note that we do not anticipate safety issues with Epidiolex because of its extremely high safety profile. Participants will take the study drug once every 12 hours and will receive a total of 4 doses. This dosing regimen has been selected based upon evidence that four doses are required for Epidiolex to reach steady-state levels and that this dosing regimen is well-tolerated (23). Cannabidiol (Epidiolex) will be flavor-masked with cherry-syrup by our research pharmacy to ensure double-blind administration. Epidiolex dose and cherry syrup will be delivered in 2 x 10 mL oral syringes.

Eligible participants will attend two residential sessions that will last 3-days/2-nights. Study procedures will take place at the Behavioral Pharmacology Research Unit's Residential Research Unit (RRU) and the Clinical Research Unit (CRU); both located on the Johns Hopkins Bayview Medical Campus. Previous studies suggest this design will provide a sufficient observation period to produce abstinence-induced withdrawal (24). Patients will be instructed to arrive at the BPRU the morning of Day 1. Research staff will contact the participant's methadone prescribing clinic to confirm the participant did not receive their dose JHMIRB eFormA 01

that morning. After collecting vitals and testing a urine sample for pregnancy and to confirm abstinence from illicit drugs, participants will receive 50% of their prescribed methadone dose, which will be prepared by the BPRU pharmacy, to consume under staff observation at BPRU. This dose will produce modest suppression of participant opioid withdrawal for an acute period of time, which will provide an opportunity for them to become acquainted with the session procedures while still ensuring they will show prominent signs of withdrawal during the study period. Initial vitals and urine testing will take place at the BPRU. The participant then will be transferred to the CRU where they will remain until the end of the 3rd day. Participants will be assessed for symptoms of opioid withdrawal and complete measures of drug craving and anxiety periodically throughout Day 1. The first dose of study drug (placebo or Epidiolex) will be administered in the afternoon (e.g., 18:00 +/- 1:00 hour) on Day 1 at the CRU.

Participants will complete withdrawal ratings on a regular basis (e.g., every 4 hours) before and after study drug administration, except for when the participant is sleeping. This schedule will be based on the pharmacokinetic profile of CBD (21). Vital signs will also be measured every time withdrawal assessments occur (Figure 1).

[figure not shown]

Figure 1. Timeline of inpatient session with approximate timing for study procedures. Gray circles indicate when measures of opioid withdrawal. craving. and anxietv are assessed.

On Day 3, participants will complete a cue-induced craving task and a Cue-concurrent Choice Task, and a Methadone Valuation Task described below. Withdrawal ratings will continue up to study discharge on Day 3 and acceptability ratings of the study drug will be collected prior to discharge. Participants will be discharged in the afternoon on Day 3, one hour after finishing the Methadone Valuation Task. At any point a participant can elect to resume regular methadone dosing and remain at the unit to complete study participation. However, participants who take their dose before beginning the Methadone Valuation Task he or she will not be able to participate in the Methadone Valuation Task. Finally, before participants leave, medical staff will collect a blood sample to be tested for liver enzyme levels. For an overview of study procedures, please reference Figure 1.

Methadone Valuation Task: The morning of Day 3, participants will complete baseline withdrawal ratings and be presented with the opportunity to take 50% of their usual methadone maintenance dose or earn money. For every 60 minutes up to 14:00 that the participant does not take the dose, they will earn a small amount of money (Total potential earnings= \$100). At the end of the period, all participants who have not yet requested their methadone dose will receive it. All Day 3 methadone doses will be 50% of the participant's prescribed dose. Participants will be required to remain on the unit under observation until JHMIRB eFormA 01 Version 3 Dated: 06/2007

17:00 to provide sufficient opportunity for peak effects of methadone to occur. At that time, all participants who show no signs of respiratory distress (SP02<96, respiration rate <8 breaths per minute) and feel safe to leave will be discharged.

All participants will be required to stay in the unit until 17:00, to prevent them from selecting methadone in order to end the study prematurely and to provide an opportunity for withdrawal to decrease in severity before they leave. The purpose of this task is to assess the objective, behavioral economic value the participant places on methadone as a withdrawal-relieving medication following accumulated exposure to Epidiolex vs. placebo. We have developed this task by translating preclinical methodology and we will use this opportunity to determine whether this task is an appropriate method to include in a formal R01 application.

Visual Probe Task: The effects of CBD on attentional bias to opioid-related cues will be evaluated with a visual probe task. In the task, a series of opioid (target) and composition-matched neutral (non-target) images are shown. Each trial begins with a fixation point before presenting a pair of images then appears on the left and right of the screen for either a short (e.g., 200 ms) or long (e.g., 500 ms) duration to assess automatic orientating and controlled attention processing, respectively. Image pairs are replaced by a probe (an arrow pointing upwards or downwards) in the location of either the neutral or opioid-related image. The probe remains on screen until the participant responds to identify the probe orientation (upwards or downwards) by pressing one of two appropriate response keys as quickly and accurately as possible (defined as a 'correct trial' if a correct response was made). Probes replace the opioid-related and neutral images equally often. The position of image type, probe location and stimulus duration is counterbalanced. Trials are displayed in a single block with each pair presented eight times, producing both critical and neutral trials. The task begins with four buffer trials. Trial order is randomized each time the task is run.

Cue-concurrent Choice Task: The effects of opioid-related cues on concurrent choice will be evaluated using a cued concurrent choice task. Participants will be instructed that they will be asked to make choices about different amounts of money that they would like to earn. Participants will be instructed that they should consider the choices carefully because they will randomly receive five of the monetary outcomes they chose. This task consists of a series of trials in which concurrent choice is evaluated between two monetary values (e.g., \$0.10 versus \$0.05). Each concurrent choice is immediately preceded by two visual stimuli presented side-by-side. On opioid trials, one image is opioid-related and the other is a paired neutral image. Opioid-related images include depictions of prescription pills or heroin and/or related drug paraphernalia. Paired neutral images are chosen to match the number of objects, color, and size of opioid images. On neutral filler trials, both images are unrelated to opioids or opioid paraphernalia (e.g., furniture pieces). All trials begin with a fixation point presented for 1000 ms in the center of the screen. The two visual stimuli then replaced the fixation point and are displayed for 2000 ms. Finally, a monetary value appears below each image and participants are instructed to select the monetary reinforcer they want to receive. Participants will receive their money choices from 20 random trials which could earn them an additional \$5. Potential earnings will be explained prior to starting the task to increase engagement with the task.

Methadone Reinduction: At the end of the Methadone Valuation Task, all participants who have not yet requested the methadone dose will receive their dose. All Day 3 methadone doses will be 50% of the participant's prescribed dose. Participants will be required to remain on the unit under observation until 17:00 to provide sufficient opportunity for peak effects of methadone to occur. At 17:00, all participants who show no signs of respiratory distress (SP02<96, respiration rate <8 breaths per minute) and feel safe to leave will be discharged. Any participant who is unable to leave will be observed until he/she is safe ot

leave or will be readmitted to the CRU one additional night. Participants will be expected to return to routine care upon methadone reinduction and study discharge.

Diet Considerations: All participants will receive a calorie-controlled, low-fat, caffeine-free diet and grapefruit juice will not be permitted at any time. Food restrictions will be in place for 1 hour before and after study drug dosing to promote consistency in absorption across administrations and individuals.

b. Study duration and number of study visits required of research participants.

The study consists of one screening visit and, if eligible, two 3-day/2-night inpatient sessions scheduled approximately 1 week apart.

c. Blinding, including justification for blinding or not blinding the trial, if applicable.

All participants will receive placebo during one of the residential sessions to provide the most rigorous test of our study hypothesis that CBD will reduce the severity of some opioid withdrawal symptoms. This within-subject design will allow us to collect the strongest data with the smallest possible sample size.

d. Justification of why participants will not receive routine care or will have current therapy stopped.

Routine Care will be suspended for the purpose of causing spontaneous withdrawal to assess the primary study outcome. Participants will be returned to routine dosing upon completion of the residential study session.

e. Justification for inclusion of a placebo or non-treatment group.

A placebo control will be used to rigorously assess the study hypotheses.

f. Definition of treatment failure or participant removal criteria.

Participants will be removed from the study if they withdraw consent or are unable to tolerate the study procedures or medication. We will remove participants if they become noncompliant with study tasks or if information emerges that suggests the study procedures or drugs are contraindicated in the study sample.

g. Description of what happens to participants receiving therapy when study ends or if a participant's participation in the study ends prematurely.

Study participation will suspend standard of care treatment while participants are completing the inpatient study sessions. Upon discharge, and in the case of the study ending prematurely, treatment as usual will resume as it was prior to the study session. Participants will be fully informed about the study design so they can make an informed decision regarding their participation.

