Following oral administration, the bioavailability of methadone ranges between 36 to 100% and peak plasma concentrations are achieved between 1 and 7.5 hours. Published reports indicate that after multiple dose administration the apparent plasma clearance of methadone ranged between 1.4 and 126 L/h, and the terminal half-life (T1/2) was highly variable and ranged between 8 and 59 hours in different studies. Methadone undergoes hepatic N-demethylation by cytochrome P450enzymes, principally CYP3A4, CYP2B6, CYP2C19 and to a lesser extent by CYP2C9 and CYP2D6. Since methadone is lipophilic, it has been known to persist in the liver and other tissues. The slow release from the liver and other tissues may prolong the duration of methadone action despite low plasma concentrations.

b. Justification and safety information if FDA approved drugs will be administered for non-FDA approved indications or if doses or routes of administration or participant populations are changed.

*Cannabidiol:* Cannabidiol is a constituent of the cannabis plant that is being actively investigated for efficacy in a wide range of potential indications (including anxiety and alcohol/substance use disorders, as evidenced by clinicaltrials.gov entries) because of its unique pharmacological mechanisms of action. Specifically, it acts as an inverse agonist on the cannabinoid CB1 and CB2, as a 5-HT1a agonist, as a positive modulator of the transient receptor vallinoid-1 (TRPV1) receptor, and as an allosteric modulator of the mu and delta opioid receptors. The only empirical human studies that have examined the effects of cannabidiol in the context of opioid use reported that cannabidiol can reduce opioid craving and associated anxiety in persons with opioid use disorder. There is preclinical support that the endocannabinoid system is influential in the expression of opioid withdrawal. Cannabinoid type 1 (CB1) receptors are co-localized with mu-opioid receptors and cannabinoid agonists and endocannabinoid catabolic enzyme inhibitors have all shown evidence for opioid withdrawal suppression. Furthermore, over the last 40 years, preclinical evidence has accumulated indicating that CBD can mitigate symptoms of opioid withdrawal and decrease opioid seeking behavior in rodent models. Together these data suggest that CBD warrants further examination as a legitimate treatment for opioid withdrawal symptoms. Safety studies have demonstrated

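### Session Procedures discharges participants one hour after the Day 3 Methadone Valuation Task, but the task and reinduction text keeps everyone until 17:00

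*Combined protocol and SAP*

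**What the plan says.** All the discharge rules are in Section 4a.

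- **Session overview (Session Procedures, the paragraph on Day 3).** "Participants will be discharged in the afternoon on Day 3, one hour after finishing the Methadone Valuation Task". No condition is attached. The same part says "Withdrawal ratings will continue up to study discharge on Day 3" and "Vital signs will also be measured every time withdrawal assessments occur", so vital signs are taken up to discharge, but no threshold is tied to leaving. It also says that participants stay in the Clinical Research Unit to the end of the third day, without a clock time.
- **Methadone Valuation Task.** The task pays for each hour up to 14:00 that the participant forgoes methadone; those who have not asked for the dose by then are given it. The hold is stated twice. The first statement runs to "17:00 to provide sufficient opportunity for peak effects of methadone to occur. At that time, all participants who show no signs of respiratory distress", and release also requires that the participant feels safe to leave. The second says that all participants are "required to stay in the unit until 17:00, to prevent them from selecting methadone in order to end the study prematurely", and adds that the wait lets withdrawal ease.
- **Methadone Reinduction.** The hold and the check appear again: "At 17:00, all participants who show no signs of respiratory distress (SP02<96, respiration rate <8 breaths per minute". There is also a fallback: "Any participant who is unable to leave will be observed until he/she is safe", or the participant is readmitted for one more night.

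Section 6a describes oral methadone: "peak plasma concentrations are achieved between 1 and 7.5 hours". No text says which discharge rule takes precedence.

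**The concern.** The overview is where staff would look for the order of events on Day 3, and it gives a specific, plausible discharge time. Someone working from it would release a participant well before the time that the detailed text requires, and before the respiratory check made at that time.

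This matters because discharge follows an opioid dose given after a period of reduced and omitted dosing, in people who may also have received CBD. Section 8a reports somnolence or sedation in up to 32% of patients on Epidiolex against 11% on placebo, and says that other CNS depressants may make it worse. The protocol gives the methadone peak as a reason for the hold, so an earlier discharge defeats a protection that the protocol set for itself.

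There is also a small statistical consequence. Withdrawal ratings run up to discharge, and Section 7a evaluates SOWS scores as a daily area under the curve, so the discharge rule sets where the Day 3 rating window closes.

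**Working it through.** The plan states no figure to reproduce. The check sets the rules side by side and does clock arithmetic.

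**Inputs**

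- Latest end of the task, and time of the end-of-period methadone dose: 14:00 (Section 4a, Methadone Valuation Task).
- Overview rule: task end + 1 h (Section 4a, Session Procedures).
- Detailed rule: 17:00 at the earliest, then the respiratory and feel-safe check (Section 4a, Methadone Valuation Task and Methadone Reinduction).
- Time to peak methadone concentration: 1 to 7.5 h (Section 6a).

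**Step 1: discharge times.** Overview rule: 14:00 + 1 h = 15:00. Detailed rule: 17:00 or later. Gap: 17:00 − 15:00 = 2 h at least.

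**Step 2: can both hold?** For task end + 1 h to equal 17:00, the task would have to end at 17:00 − 1 h = 16:00. It ends at 14:00. The afternoon timing in the overview fits both 15:00 and 17:00; the one-hour interval does not.

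**Step 3: observation after a 14:00 dose.**

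| Rule | Discharge | Hours after a 14:00 dose |
|---|---|---|
| Overview | 15:00 | 15 − 14 = 1 |
| Detailed | 17:00 or later | 17 − 14 = 3 or more |

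**Step 4: against the stated peak.** One hour coincides with the lower limit of 1 to 7.5 h. Three hours lies inside the range but does not cover it: 14:00 + 7.5 h = 21:30, which is 4.5 h after 17:00.

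**Step 5: the respiratory check.** The detailed text makes it at 17:00. The overview neither mentions nor denies it. A participant discharged at 15:00 would have left before it was due, so the lost check follows from the timing conflict and is not a second contradiction.

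**Separate, lower-grade note on Section 8.** Sections 8a and 8b rate the interaction risk as low because CBD rises while methadone falls. On the example schedule (first dose at 18:00 on Day 1, then every 12 h), the four doses fall at 18:00 on Day 1, 06:00 and 18:00 on Day 2, and 06:00 on Day 3. A 14:00 methadone dose then comes 14 − 6 = 8 h after the fourth CBD dose, and sooner if it is requested earlier in the task. If the ±1 h given for the first dose also applies to the fourth, the 8 h becomes 7 to 9 h. The rationale does not describe Day 3, when methadone is reintroduced.

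**The case against.** The strongest reply is that the intent is plain. The 17:00 hold is stated three times, with reasons, in the paragraphs that govern the task and the return to methadone. The overview points forward to the task description and itself keeps participants on the unit to the end of the third day. Harm would require staff to follow one summary clause over three explicit instructions. Vital signs are taken with each rating up to discharge, and no methadone dose exceeds the participant's routine dose. All of this stands. It lowers the likelihood of harm and shows which rule should survive, but it does not remove the conflicting instruction.

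Four stronger readings are tempting, and the documents do not support them.

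- *The overview cancels the respiratory check.* It is silent on the check; only the times conflict.
- *The hours of observation can be turned into a share of peaks, or of participants, missed.* The 1 to 7.5 h figure is a range of times with no distribution, so it gives no such risk.
- *Everyone receives methadone at or just before 14:00 on Day 3.* The overview lets participants resume methadone at any point and bars those dosed before the task from taking part in it. When such participants are dosed on Day 3 is not stated.
- *An early taker could leave an hour after dosing, even in the morning.* This would need finishing to mean taking the dose, and the overview places discharge in the afternoon.

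On the Section 8 note, the reply has some weight. The Day 3 dose is half the prescribed dose, Section 6b cites tolerability of CBD with fentanyl, and adverse events are monitored. Section 6a puts the peak after 750 mg at 5 to 6 h, which is about 11:00 to 12:00 after a 06:00 dose and so before a 14:00 methadone dose. A methadone dose requested earlier could fall nearer that peak. The note remains a comment on incomplete wording.

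**Conclusion.** The discharge sentence in the session overview is wrong as written and must be corrected. It conflicts with the rest of Section 4a by at least 2 h: 15:00 against 17:00 or later, or 1 h against at least 3 h after a 14:00 dose. Followed literally, it would also release participants before the respiratory and feel-safe check. Confidence in this is high.

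The figures assume that the task ends at 14:00, the latest time the protocol gives. Figure 1 is not available here; it might show a discharge time, but it could not make the two written rules agree. That 17:00 is intended is an inference from the text, though a strong one.

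A reader might infer that the trial's real procedure is to discharge one hour after methadone, or that the 17:00 hold covers the whole methadone peak. The first is unlikely given the three statements of the hold, and the second does not follow from the stated range. The conclusion is only that one sentence contradicts the protocol's own safety rule. The Section 8 point is a separate wording matter, held with moderate confidence and resting on the example dosing times.

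**What to change.** Replace the overview's discharge sentence with the rule in the detailed text. For example: *On Day 3 participants stay on the unit under observation until at least 17:00. They are then discharged only if they meet the respiratory and feel-safe criteria given under Methadone Reinduction; anyone who does not is observed further or stays another night.* If Figure 1 shows a discharge time, check that it agrees.

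The cost is one sentence in a protocol amendment, with no new data, visits or analyses. The length of the hold and the clinical thresholds remain for the investigators to decide.

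As a separate and lower priority, add a line to Sections 8a and 8b acknowledging that methadone is reintroduced on Day 3 within about 8 h of the last CBD dose on the example schedule, and giving the reasoning for that period.
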